#### **4.2.1.2 Blinding of Study Vaccine**

Study vaccine will be administered in observer blinded fashion (described in [section 4.2.1.1](#)).

For this study using IRT, vaccine will be packed using the ‘scrambled pack numbering’ methodology. All vaccine outer packs will look identical, and are blinded at the kit level. Each pack will be given a unique pack number. IRT will know the content of each pack. Once the unblinded site staff performing the vaccination has opened the outer pack, this person is unblinded for that subject.

#### **4.2.2 Planned Unblinding for Interim Analysis**

A formal interim analysis of immunogenicity is planned when Day 43 immunogenicity data are available for all subjects (excluding those lost to follow-up or withdrawn for other reasons). To preserve the integrity of the study, the interim analysis will be handled by an independent statistician and an independent programmer from Clinical Research Organization (CRO) who are not involved in day-to-day study activities and independent from Sponsor. The unblinded protected data snapshots for interim analysis will be restricted to only unblinded individuals responsible for the interim analyses. The interim analysis results will be available to a restricted number of individuals such as select members of Sponsor senior management not directly working on this study, who will be identified prior to the interim analysis. As the results may be transmitted to the Biomedical Advanced Research and Development Authority within the Department of Health and Human Services (HHS/BARDA), Sponsor personnel engaged in discussions with HHS may also be made aware of results. No individuals with access to study results will be involved in day-to-day study activities or decisions regarding individual subject assessments. Investigators, site staff, Sponsor personnel, CRO personnel, and the serology laboratory will remain blinded to the clinical study data and subjects’ individual study arm assignment until final data from all termination visits are locked, including both individual subject serology results and serology results by group.

#### **4.2.3 Planned Unblinding for Final Analysis**

The study will be fully unblinded after final database lock.

### **5. SAMPLE SIZE AND POWER CONSIDERATIONS**

Sample size/power considerations are included in the study protocol. Technical details including statistical assumptions and software are given in a separate sample size memo authored by the study Biostatistician. In the same document, a statistical co-reviewer verified and documented the sample size/power considerations. This document was completed prior to finalization of the protocol, see [Appendix A](#) for reference.

For details please refer to [section 7.4.2.3 of the Protocol](#).

## 6. DETERMINATION OF PROTOCOL DEVIATIONS

### 6.1 Definition of Protocol Deviations

Deviations from the protocol will be assessed as ‘minor’ or ‘major’. Major (reportable) protocol deviations (PDs) from the protocol that will lead to the exclusion of the subject or part of the subject’s data from the analysis set will be identified a priori. Major PDs are defined as those deviations from the protocol likely to have an impact on the perceived immunogenicity and/or safety of study treatments. The impact of major PDs on the immunogenicity and/or safety results will be investigated by assessing the robustness of the study results. The final determination of major PDs and the exclusion of subjects from each of the analysis populations will be made prior to unblinding the database.

All major PDs will be classified into the following categories, but not all deviations listed below will necessarily be declared a major PD:

- Informed Consent
- Inclusion/Exclusion criteria
- Withdrawal Criteria
- Investigational Product (IP) Admin/Study Treat
- Disallowed Medications
- Adverse Event (AE)/ Serious Adverse Event (SAE)
- Visit Schedule
- Procedure/Tests

Major protocol deviations and any action to be taken regarding the exclusion of subjects or affected data from specific analyses are defined in [Table 6.1-1](#).

**Table 6.1-1: Exclusion from Specific Analyses due to Major Protocol Deviations**

Major Protocol Deviation	Action to be Taken For Analysis
Subject was not administered any study vaccine	Exclude from all population set
Serological results are not available	Exclude from Full Analysis Set (FAS) Exclude from Per Protocol Set (PPS)
Obvious deviation from laboratory manual or error in laboratory data	Exclude from FAS Exclude from PPS
Subject did not provide any post-vaccination unsolicited safety data	Exclude from Unsolicited Safety Set
Subject did not provide any post-vaccination	Exclude from Solicited Safety Set

Major Protocol Deviation	Action to be Taken For Analysis
solicited safety data	
Randomization failure	Exclude from PPS
Randomization code was broken	Exclude from PPS
Vaccination not according to protocol	Exclude from PPS
Administration of forbidden vaccine	Exclude from PPS
Subject did not meet entry criteria	Exclude from PPS
Subject had contraindication for a subsequent study vaccination but was vaccinated	Exclude from PPS
Administration of prohibited medication	Exclude from PPS
Underlying medical condition prohibited by the protocol	Exclude from PPS
Concomitant infection related to the vaccine which may influence immune response	Exclude from PPS
Did not comply with study vaccination schedule	Exclude from PPS
Did not comply with blood draw schedule	Exclude from PPS

Note: PPS = Per Protocol Set; FAS = Full Analysis Set

The following PD summaries will be provided:

- Number and percentage of subjects with a major protocol deviation by type of deviation and vaccine group

A by-patient listing of protocol deviations will be provided.

## **6.2 Determination of Protocol Deviations**

Prior to unblinding, a PD report will be provided to the Clinical Study Team (CST) consisting of medical, clinical, and operational team members from the Sponsor and CRO for review on an ongoing basis during the study. The PDs review is part of the Data Listing Review process.

After the review, the CST team is responsible for assessing the impact of PDs on the immunogenicity and safety data for study subjects from medical and clinical perspectives. The PDs will be identified and categorized to determine subjects to be excluded from analysis populations according to the PDs specification and [Table 6.1-1](#).

Details of PD review procedure will be provided in the Medical Monitoring Plan and Data Listing Review Manual.

### 6.3 Exclusions of Individual Values for Safety Analysis

Some local and systemic adverse events (AEs) will be directly measured by the subject and will not be subject to a reconciliation process, even if they are biologically implausible. Therefore these implausible measurements will be removed from the analysis but included in listings. Implausible measurements are summarized in the [Table 6.3-1](#) below:

**Table 6.3-1: Implausible Solicited Adverse Events**

Parameter	Implausible measurements
Body temperature	$\leq 33^{\circ}\text{C}$ or $\geq 42^{\circ}\text{C}$
Erythema	Measurements $\geq 900$ mm Measurements $< 0$ mm
Induration	Measurements $\geq 500$ mm Measurements $< 0$ mm
Ecchymosis	Measurements $\geq 500$ mm Measurements $< 0$ mm

## **7. ANALYSIS SETS**

### **7.1 All Enrolled Set**

All screened subjects who provide informed consent and provide demographic and/or other baseline screening measurements, regardless of the subject's randomization and vaccination status in the study, and received a subject ID.

### **7.2 Exposed Set**

All subjects in the All Enrolled Set who receive a study vaccination.

### **7.3 Full Analysis Set (FAS), Immunogenicity Set**

All subjects in the All Enrolled Set who:

- actually receive at least one dose of study vaccination, and
- provide at least one immunogenicity result at relevant timepoints.

FAS will also be defined by timepoint and objective:

- FAS-1 will include all subjects who received at least one dose of study vaccine and provide at least one immunogenicity result at Day 1 and Day 43.
- FAS-2 will include all subjects who received at least one dose of study vaccine and provide at least one immunogenicity result at Day 1 and Day 22.
- FAS-3 will include all subjects who received at least one dose of study vaccine and provide at least one immunogenicity result at Day 1 and Day 183.

In case of vaccination error, subjects in the FAS will be analyzed "as randomized" (i.e., according to the vaccine a subject was designated to receive, which may be different from the vaccine the subject actually received). Any subject who received the wrong vaccination will not be excluded from the FAS.

Subjects randomized in the wrong stratum will be analyzed in the stratum in which they were randomized (i.e., analyze subject in wrong stratum).

If a subject is unblinded during the study, he/she will be included in the FAS.

### **7.4 Per Protocol Set (PPS), Immunogenicity Set**

All subjects in the FAS Immunogenicity who:

- Correctly receive the vaccine (i.e., receive the vaccine to which the subjects is randomized and at the scheduled time points).

- Have no major protocol deviations leading to exclusion (see [section 6.1](#)) as defined prior to unblinding / analysis.
- Are not excluded due to other reasons (e.g. subjects who withdrew informed consent) defined prior to unblinding or analysis (see [section 6.2](#))

In case of vaccination error, subjects in the PPS will be analyzed “as randomized” and the subject who received the wrong vaccination will be excluded from the PPS. If a subject receives a vaccine from the wrong kit number, but the same as the one the subject was randomized to, the subject will not be removed from the PPS.

Subjects randomized in the wrong stratum will be excluded from the PPS.

If a subject is unblinded during the study, except for SUSAR, he/she will be excluded from the PPS.

Similarly to FAS, PPS will also be defined per objective and timepoint:

- PPS-1 will include all subjects who are in FAS-1 and correctly received study vaccine, have no major protocol deviations leading to exclusion and are not excluded due to other reasons as defined prior to unblinding / analysis.
- PPS-2 will include all subjects who are in FAS-2 and correctly received study vaccine, have no major protocol deviations leading to exclusion and are not excluded due to other reasons as defined prior to unblinding / analysis.
- PPS-3 will include all subjects who are in FAS-3 and correctly received study vaccine, have no major protocol deviations leading to exclusion and are not excluded due to other reasons as defined prior to unblinding / analysis.

Exclusions will be considered by objective/time point, i.e., sometimes not all data of a subject but only part of the subject's data will be removed from the PPS analysis.

## **7.5 Safety Set**

### Solicited Safety Set

All subjects in the Exposed Set who have gone through any assessment of local and systemic site reaction and/or assessment of any use of analgesics/antipyretics.

### Unsolicited Safety Set

All subjects in the Exposed Set who have gone through any adverse event assessments i.e., a subject does not have to have any adverse events to be included in this population.

### Overall Safety Set

All subjects who are in the solicited safety set and/or in the unsolicited safety set.

Subjects providing only 30 minutes post-vaccination safety data will also be reported separately in a 30-minute post-vaccination safety analysis.

In case of vaccination error, subjects will be analyzed as “treated” (i.e., according to the vaccine a subject receives, rather than the vaccine to which the subject is randomized).

Subjects randomized in the wrong stratum will be reassigned to the correct stratum and will be analyzed using corrected stratum for all safety sets (i.e., solicited safety set, unsolicited safety set and overall safety set). If a subject is unblinded during the study, he/she will be included in all the safety sets.

#### **7.5.1 Restricted Safety Set**

Not applicable.

#### **7.6 Other Analysis Set**

Not applicable.

## **8. GENERAL ISSUES FOR STATISTICAL ANALYSES**

### **8.1 Adjustment for Covariates**

Adjusted estimates of geometric mean titers (GMTs), and their associated 95% confidence intervals (CIs) at Day 43 will be determined using analysis of covariance (ANCOVA) with factors for lot, age groups (18 to <65,  $\geq 65$ ), center and a covariate for the effect defined by the log-transformed pre-vaccination antibody titer. Influenza-antibody GMTs (Day 43), associated two-sided 95% CIs and median, minimal, and maximal area/titer values will be determined and presented together with N (number of subjects), by lot (for the first primary objective).

This model will include only immunogenic data from the 3 lots of aH5N1.

If the statistical model does not converge due to the factor “center”, a model without center effect will be fitted instead.

The placebo group titers/concentrations will be summarized without any adjustment (i.e. unadjusted GMTs and percentages).

Binary data tables will show adjusted percentages and adjusted “between-group” differences.

### **8.2 Handling of Dropouts, Missing Data**

First-line analyses will be without missing values.

To minimize the effect of dropouts and missing data the study period will be divided into time intervals for statistical analysis of immunogenicity.

#### **8.2.1 Safety Data**

For unsolicited adverse events, the entire study period will be divided into the following intervals: Day 1-22, Day 23-43, Day 1-43, Day 44-387, Day 1-387.

For solicited adverse events, the solicited study period 30 min - Day 7 after each vaccination will be divided into: 30 min, Day 1-3 (with and without the 30-minute interval), Day 4-7, and Day 1-7 (with and without the 30-minute interval).

No imputation of missing solicited or unsolicited AEs will be used. The percentage of subjects with missing solicited AE assessments and missing safety phone calls or safety assessment, including subjects who discontinued the study, will be reported for each time period.

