Immunogenicity Endpoints: The immunogenicity endpoints will be based on hemagglutinin inhibition (HI) antibody responses to the H5N1 vaccine strain. 
- GMT at Day 43 by lot- GMT at Day 1, Day 22, Day 43 and Day 183 by vaccine group (aH5N1c or placebo) and by age cohort (18 to <65 years of age and ≥65 years of age; 18 to <60 years of age and ≥60 years of age)- Percentage of subjects with HI titer ≥ 1:40 at Day 1, Day 22, Day 43 and Day 183 by vaccine group (aH5N1c or placebo) and by age cohort (18 to <65 years of age and ≥65 years of age; 18 to <60 years of age and ≥60 years of age)- Percentage of subjects achieving seroconversion (defined as: HI titer ≥1:40 for subjects negative at baseline [HI titer <1:10]; or a minimum 4-fold increase in HI titer for subjects positive at baseline [HI titer ≥1:10]) at Day 22 and Day 43 by vaccine group (aH5N1c or placebo) and by age cohort (18 to <65 years of age and ≥65 years of age; 18 to <60 years of age and ≥60 years of age)- Geometric mean ratio (GMR) at Day 1, Day 22, Day 43 and Day 183 by vaccine group (aH5N1c or placebo) and by age cohort (18 to <65 years of age and ≥65 years of age; 18 to <60 years of age and ≥60 years of age)		
Safety Endpoints: The endpoints for assessing safety and tolerability are as follows: 
- Percentages of subjects with solicited local, solicited systemic, and other adverse events as measured for 7 days following each vaccination within each vaccine group.- Percentages of subjects with unsolicited AEs reported through 21 days after last vaccination within each vaccine group.- Percentages of subjects reporting SAEs, AESIs, NOCD, AEs leading to vaccine/study withdrawal, medically attended AEs, and concomitant medications associated with these events as collected from Day 1 to Day 387 within each vaccine group.		

Name of Sponsor: Seqirus, Inc.	Protocol number: V89_18	BB-IND No. 13,536

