After each vaccination, all subjects will remain under medical supervision at the study site for at least 30 minutes to be monitored and evaluated for AEs. Subjects will be instructed on the measurement of local and systemic solicited AEs, including body temperature, and on the completion of the diary cards.

The diary cards will collect solicited and unsolicited AEs, and medication/vaccinations given from Day 1 to Day 7 (inclusive) and from Day 22 to Day 28 (inclusive). From Day 8 to 21 and from Day 29 to 42, only unsolicited AEs, solicited AEs that continue beyond Day 7 or 28, respectively, and medications/ vaccinations will be collected at the time of return to the clinic on Day 22 or 43, respectively.

In addition to these safety data, from Day 1 through Day 387 (inclusive) serious adverse events (SAEs), adverse events of special interest (AESIs), new onset of chronic disease (NOCD), AEs leading to vaccine/study withdrawal, medically attended AEs, associated concomitant medications for any of these events, and all vaccinations will be recorded. For full list of AESIs see [appendix A](#). These data will be captured through the diary card, by interview of the subject, and by review of available medical records.

Blood will be drawn from each subject for immunogenicity assessments before each vaccination (Day 1 and Day 22) and also drawn at clinic visits on Day 43 and Day 183. Blood drawn will be evaluated for antibody responses as measured by HI antibody responses and possibly also microneutralization (MN) antibody responses.

An interim analysis of immunogenicity will be performed for all subjects through the Day 43 visit. Site staff and Sponsor personnel involved in study conduct will remain blinded to treatment assignments for this interim analysis.

The final analysis will be performed when all data up to the study end (Day 387) are available. Analysis will be done on fully unblinded data by the Sponsor and all data will be presented in the final, cumulative study report. A Data Monitoring Committee (DMC) will not be used for this study.

To maintain the observer-blind design of the study for the two vaccine doses (Day 1 and Day 22), the roles and responsibilities of blinded and unblinded team members will be defined and maintained throughout the study. Safety assessments and study related procedures and monitoring thereof must be performed by blinded team members.

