7.1.4 Safety Endpoints

The measures for assessing safety and tolerability are as follows:

- Percentages of subjects with solicited local, solicited systemic and other AEs as measured for 7 days (inclusive) following each (1st and 2nd) and any (1st or 2nd) vaccination, by vaccine group (and calculated for several time intervals after vaccination⁷: 30 minutes, 1 to 3 days (without 30 min), 4 to 7 days, and 1 to 7 days (without 30 min), and 1 to 3 days (including 30 minutes) and 1 to 7 days (including 30 minutes).
- Percentages of subjects with any unsolicited AEs reported through 21 days after each (1st and 2nd) and any (1st or 2nd) vaccination by vaccine group.
- Percentages of subjects reporting SAEs, AESIs, NOCD, AEs leading to vaccine/study withdrawal, and medically attended AEs, and concomitant medications associated with these events as collected from Day 1 to Day 387, by vaccine group.

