#### Level 5: Solicited adverse events, occurrence of at least one event by category (local, systemic) and interval.

The **occurrence of at least one solicited adverse event** is defined as “any” for a subject if he/she reports greater than “none” for qualitatively assessed solicited systemic AEs and/or  $\geq 25$  mm for erythema, ecchymosis and induration for the respective event and “none” otherwise. The occurrence of at least one solicited adverse event (i.e., none versus any) will be summarized by category (i.e., local, systemic, any), by vaccine group, by vaccination (after each vaccination and after any vaccination) and by time interval.

Medications to treat or prevent pain or fever will be summarized by frequencies and percentages of subjects reporting use of the medications by interval 30 min, Day 1 – 3 (excluding 30 minutes after vaccination), Day 4 – 7, Day 1 – 7 (excluding 30 minutes after vaccination).

For details please refer to [section 7.1.1 of the Protocol](#).

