### **13.3 Unsolicited Adverse Events**

The first-line analysis will use unsolicited adverse event data from all reporting sources combined. A second-line analysis will encompass the analysis of unsolicited adverse events by source.

All the unsolicited adverse events occurring during the study, judged either as probably related, possibly related, or not related to vaccination by the investigator, will be recorded. The original verbatim terms used by investigators to identify adverse events in the case report forms (CRFs) will be mapped to preferred terms using the MedDRA dictionary. The unsolicited adverse events will then be grouped by MedDRA preferred terms into frequency tables according to system organ class. Adverse events judged by the investigator as at least possibly related to study vaccine will be summarized by vaccine group, according to system organ class and preferred term within system organ class. When an unsolicited adverse event occurs more than once for a subject, the maximal severity and strongest relationship to the vaccine group will be counted.

Only vaccine-emergent adverse events (see [section 8.7](#) for definition) will be analyzed, i.e., excluding those after a subject has given informed consent but before vaccination. The selection of unsolicited adverse events and the assignment to time intervals will be done by day of onset and not by days ongoing/persisting.

The summaries will be presented by period of onset and will include frequency distributions of the different adverse events:

- Onset between Day 1 and Day 22.
- Onset between Day 23 and Day 43.
- Onset between Day 1 and Day 43.
- Onset between Day 44 and study termination.
- Onset between Day 1 and study termination.

The analysis of unsolicited adverse events comprises the following categories:

- Any unsolicited adverse event.
- Possibly or probably related unsolicited adverse events.
- Unsolicited adverse events leading to death.
- Serious adverse events.
- Possibly or probably related serious adverse event.
- Unsolicited adverse events leading to premature withdrawal from study.
- Unsolicited adverse events leading to dose change in study vaccination.
- Unsolicited adverse events leading to new onset of chronic disease (NOCD).
- Unsolicited adverse events of special interest (AESI), see [Appendix A of the protocol](#)
- Medically attended adverse events.

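### The SAP's unsolicited-AE intervals put the day of dose 2 in the first interval, so no summary it lists delivers the protocol's 21-day endpoint after the second vaccination

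*SAP*

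**What the plan says.** Evaluating safety and tolerability is a primary objective. Protocol 7.1.4 lists among its measures the percentage of subjects with "any unsolicited AEs reported through 21 days after each (1st and 2nd) and any (1st or 2nd) vaccination". The protocol synopsis words the endpoint more broadly, as "unsolicited AEs reported through 21 days after last vaccination within each vaccine group".

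Both documents schedule the doses on Day 1 and Day 22. SAP 8.2.1 divides the study for unsolicited AEs into "Day 1-22, Day 23-43, Day 1-43, Day 44-387, Day 1-387". SAP 13.3 repeats these cuts, with "Onset between Day 23 and Day 43" as the only interval confined to the time after dose 2, and states that "the assignment to time intervals will be done by day of onset and not by days ongoing/persisting".

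On presentation, SAP 13.3 says only: "The summaries will be presented by period of onset". For solicited AEs, by contrast, SAP 13.2 (Level 5) summarises occurrence "by vaccination (after each vaccination and after any vaccination) and by time interval".

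SAP 8.7 has two relevant derivation rules. An AE is linked to the latest vaccination before it. A variable separates onset before from onset after injection, but it is defined only for the date of the first injection. SAP 17 refers to a separate shell document for the full table list.

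**The concern.** An unsolicited AE that starts on Day 22 after the second injection falls in Day 1-22. It is therefore shown in the dose 1 period, and the post-dose-2 interval leaves out the day of injection. The first-dose figure is affected as well, because it absorbs these events.

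This is not a convention applied evenly to both doses. The SAP counts the day of dose 1 in the first interval, and the diary periods in Protocol 3.1 (Day 1 to 7 and Day 22 to 28) put Day 22 with dose 2.

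The day of injection is a natural time for acute events. The listed local and systemic reactions are covered by the solicited analysis, but other same-day events, such as a hypersensitivity reaction, enter as unsolicited AEs. So do solicited reactions missing from the diary and first reported at the visit (Protocol 3.4.1). A reader comparing the first and second dose would see post-dose-2 events of this kind in the wrong period.

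**Working it through.** **Inputs**
- Dose 2 on nominal Day 22 (Protocol 3.1; SAP 3).
- Visit 2 window 21-30 days after dose 1, so dose 2 on actual Day d with d = 22 to 31 (Protocol Table 2; SAP Table 3-2).
- Day 43 visit window 21-30 days after dose 2 (same tables).
- SAP intervals Day 1-22 (22 days) and Day 23-43 (21 days).

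**Schedule check.** 22 + 21 = 43, which agrees with Protocol 6.3, where Day 43 is 21 days after the second vaccination. For dose 1, 1 + 21 = 22, so Day 1-22 is exactly the day of dose 1 plus 21 days.

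**Nominal schedule (d = 22)**
- If dose 2 is treated as the SAP treats dose 1, the window is Day d to d + 21 = Day 22-43, 22 days. Day 23-43 holds 21 of them; Day 22 is missing.
- If 21 days are counted including the day of dose 2, the window is Day 22-42. Day 23-43 holds 20 of these 21 days, lacks Day 22 and adds Day 43.

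The SAP does not say whether its days are calendar study days or stand for visits, so both readings were worked through.

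**Visit-anchored reading.** The second interval runs from d + 1 to the Day 43 visit, which falls on d + 21 to d + 30.
- Overlap with Day d to d + 21: days d + 1 to d + 21, i.e. 21 of 22 for every d from 22 to 31. The missing day is always the day of dose 2.
- Days before dose 2 included: 0.
- Days beyond the 21-day limit included: 0 to 9, depending on when the Day 43 visit takes place.

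**Calendar reading**
- Overlap = min(43, d + 21) − max(23, d) + 1.
- Days before dose 2 inside Day 23-43 = max(d − 23, 0).
- Window days after Day 43 = d − 22.
- Extreme case d = 31: overlap = 43 − 31 + 1 = 13 of 22; days before dose 2 = 31 − 23 = 8; window days after Day 43 = 31 − 22 = 9.
- For d = 23 to 31 the day of dose 2 itself lies inside Day 23-43, but the interval then cuts off the end of the 22-day window and, from d = 24, also includes days before dose 2.

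**Exact matches.** On the calendar reading with the 22-day window, no SAP interval matches for any d from 22 to 31. With the 21-day window, Day 23-43 matches only when d = 23.

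**Which reading is likelier.** Protocol 7.4.3 bases the intervals on the time and events schedule. Protocol 5.4 describes three weeks after each vaccination as Day 1 to Day 43. Footnote 7, attached to the solicited intervals, refers the second vaccination to the time and events table. With the Day 43 visit window, these lean toward visit anchoring.

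**Is the endpoint delivered elsewhere?** SAP 13.3 lists no unsolicited summary by vaccination number, and nothing listed in the SAP uses the link to the latest vaccination in SAP 8.7. SAP 13.3 also does not restrict the Day 23-43 percentages to subjects who received dose 2. On the nominal schedule, Day 1-43 does deliver the any-vaccination part of Protocol 7.1.4 and the synopsis endpoint.

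**The case against.** The strongest case against has five parts.

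- **The endpoint does not say that the injection day counts.** Day 23-43 is the 21 days following nominal Day 22. That is a possible reading of the words, but the SAP does not apply it to dose 1, the diary periods do not follow it, and it would leave post-injection onsets on the day of dose 2 in no post-dose-2 summary.
- **The protocol leaves the cuts to the SAP.** Protocol 7.4.3 asks for disjoint intervals and lets the analysis plan set their limits, so Day 22 must fall on one side. Some Day 22 onsets precede the injection and belong with dose 1. Both points are true, but the latitude does not withdraw the endpoint in Protocol 7.1.4, and the SAP has no timing rule that separates the two kinds of Day 22 onset.
- **SAP 8.7 already attributes each AE to the latest dose, and the shells may contain a per-dose table.** The rule exists, but no summary listed in the SAP uses it. A per-dose table in the shells cannot be ruled out; if there is one, SAP 13.3 should say so.
- **The larger figures rest on the less likely reading.** This stands. The result of 13 out of 22 days applies only to calendar days and the latest permitted dose 2, and the documents give no distribution of dose 2 days. The one-day gap does not depend on it.
- **The consequence is small.** This also stands. The analysis is descriptive, all arms are cut alike, no event is lost overall, solicited and 30-minute reactions are analysed per vaccination, and AE listings by subject are planned.

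**Conclusion.** The concern holds. No summary listed in the SAP delivers the second-dose part of the unsolicited-AE endpoint in Protocol 7.1.4, and post-injection onsets on nominal Day 22 are shown with dose 1.

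The firm size is one day, the day of dose 2: 21 of 22 window days are covered, or 20 of 21 if the window is 21 days including the day of dose 2. This applies on the nominal schedule and, if the days stand for visits, to every subject given dose 2 at Visit 2. Any further shift arises only if the days are calendar days and dose 2 is later than Day 22.

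The conclusion assumes that the day of injection belongs to its own post-dose period, as the SAP treats dose 1 and the diary treats both doses. It covers only summaries named in the SAP. How many AEs would move cannot be determined from the documents. No hypothesis test or success criterion is affected; the case for correcting it is that a stated safety endpoint should be produced as defined.

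**What to change.** In SAP 8.2.1 and 13.3, define the intervals from each subject's actual vaccination dates:

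- (a) dose 1 through 21 days after dose 1, or until immediately before dose 2 if that is earlier;
- (b) dose 2 through 21 days after dose 2, with dose 2 recipients as denominator;
- (c) first vaccination through 21 days after the last vaccination received, which matches the synopsis endpoint;
- (d) thereafter to study end, and the whole study.

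Apply the latest-vaccination rule of SAP 8.7 in these summaries and extend its before/after-injection flag to the day of dose 2. If that timing was not recorded, assign same-day onsets to dose 2.

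The cost is SAP wording and a small derivation; Protocol 5.5 already requires the date and time of vaccination to be documented. There are two side effects to state in the SAP. Under the fallback, some AEs that began on the day of dose 2 before the injection may be attributed to dose 2. When dose 2 is late, onsets between the end of (a) and dose 2 appear only in (c) and the whole-study summary. That gap is max(d − 23, 0) full days: none for dose 2 on Day 22 or 23, and 8 (Day 23-30) for dose 2 on Day 31.
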